11.2 Serious Adverse Experiences (SAE)

An SAE is defined as any AE occurring at any dose that results in any of the following outcomes:

- death
- a life-threatening adverse experience

Version #: 2.8 Version Date: 11/6/2020 Page 21 of 30

- inpatient hospitalization or prolongation of existing hospitalization
- a persistent or significant disability/incapacity

Other important medical events may also be considered an SAE when, based on appropriate medical judgment, they jeopardize the subject or require intervention to prevent one of the outcomes listed.

11.2.1 Serious Adverse Experience Reporting

Study sites will document all SAEs that occur (whether or not related to study drug) per Lifespan IRB guidelines. The collection period for all SAEs will begin after informed consent is obtained and 28-days after last administration of Maraviroc.

In accordance with the Pfizer contractual terms, standard operating procedures and policies of the Lifespan Institutional Review Board (IRB) the Investigator or one of the study members will report SAEs to the IRB. SAE and AE documentation will occur in REDCap.

12 DISCONTINUATION AND REPLACEMENT OF SUBJECTS

12.1 Early Discontinuation of Study Drug

A subject may be discontinued from study treatment at any time if the subject or the investigator feels that it is not in the subject's best interest to continue. The following is a list of possible reasons for study treatment discontinuation:

- Subject withdrawal of consent (or assent)
- Subject is not compliant with study procedures
- Adverse event that in the opinion of the investigator would be in the best interest of the subject to discontinue study treatment, including stoppage criteria for orthostatic hypotension
- Protocol violation requiring discontinuation of study treatment
- Drug supplier (Pfizer) request for early termination of study, after which study drug cannot be reasonably provided to subjects at no cost to them
- Positive pregnancy test (females)
- Pursuit of comfort measures only, inpatient hospice referral or transfer to inpatient hospice facility

Version #: 2.8 Version Date: 11/6/2020 Page 22 of 30

If a subject is withdrawn from treatment due to an adverse event, the subject will be followed and treated by the study team until the abnormal parameter or symptom has resolved or stabilized.

Subjects who are discharged from the hospital will not continue taking Maraviroc outside the hospital. Early completion prior to seven days of therapy will not be considered early withdrawal from the study. All subjects who discontinue study treatment will undergo an early discontinuation visit as soon as possible and will be encouraged to complete all remaining scheduled research labwork (except in the instance of comfort measures and hospice). Subjects are free to withdraw from participation at any time, for any reason, specified or unspecified, and without prejudice.

Reasonable attempts will be made by the investigator to provide a reason for subject withdrawals. The reason for the subject's withdrawal from the study will be specified in the subject's source documents.

12.3 Withdrawal of Subjects from the Study

A subject may be withdrawn from the study at any time if the subject or the investigator feel that it is not in the subject's best interest to continue.

All subjects are free to withdraw from participation at any time, for any reason, specified or unspecified, and without prejudice.

Reasonable attempts will be made by the investigator to provide a reason for subject withdrawals. The reason for the subject's withdrawal from the study will be specified in the subject's source documents. As noted above, subjects who discontinue study treatment early should have an early discontinuation visit. Refer to Section 10 for early termination procedures.

12.4 Replacement of Subjects

Subjects who withdraw from the study treatment will not be replaced. Subjects who are discharged from the hospital due to clinical improvement prior to completing the 7-day course will not be replaced. Subjects may be added to the study to replace subjects with incomplete data (said subjects will continue to receive Maraviroc) stemming from research bloodwork processing errors due to mishandling of shipments resulting in compromised fidelity of samples.

13 PROTOCOL VIOLATIONS

A protocol violation occurs when the subject or investigator fails to adhere to significant protocol requirements affecting the inclusion, exclusion, subject safety, and primary endpoint criteria. Protocol violations for this study include, but are not limited to, the following:

- Failure to meet inclusion/exclusion criteria
- Use of a prohibited concomitant medication
- Non-compliance with study drug regimen, including dose-reduction protocol

Version #: 2.8 Version Date: 11/6/2020 Page 23 of 30

• Failure to comply with Good Clinical Practice (GCP) guidelines will also result in a protocol violation. The Investigator will determine if a protocol violation will result in withdrawal of a subject.

When a protocol violation occurs, it will be discussed with the Investigator and a Protocol Violation Form detailing the violation will be generated. This form will be signed by the Investigator and forwarded to the IRB. Documentation of Protocol Violations will be stored on IRB.net.

14 DATA SAFETY MONITORING

Despite Maraviroc being well-tolerated without significant side effects in previous trials and its current use in patients with HIV, vigilance and at minimum daily audits of subjects' objective and subjective response to treatment is required given the aggressiveness of SARS-CoV-2. The trial team will be responsible for eliciting adverse events and reviewing inpatient documentation daily. The trial team has specifically pre-defined possible adverse events. However, given the multitude of possible adverse events, the study protocol is not able to define all of them in advance as many may not lend themselves to satisfactory definition during trial design. Adverse events will be monitored by the Investigators and Medical Monitor during the study.

14.1 POSTURAL DIZZINESS AND ORTHOSTATIC HYPOTENSION

In healthy volunteers, orthostatic hypotension four hours after administration of Maraviroc was observed in subjects receiving high doses (600mg or more) of Maraviroc versus placebo. Per package labeling, it is recommended that users who also take an antihypertensive medication be asked about symptoms of orthostatic hypotension. Of note, in two Phase 3 trials, 8% of patients in active (exposure adjusted rate of 14.1 per 100 pt-yrs) and placebo drug groups described postural dizziness, but the rate of discontinuation due to syncope or orthostatic hypotension between the Maraviroc group and the placebo were reported at 0.5%. Of the 840 subjects who received one dose of Maraviroc, 2 discontinued therapy (1 due to syncope, 1 due to orthostatic hypotension, with an exposure adjusted rate of .07 per 100 pt-yrs). ¹⁸ It is possible that the rate of dizziness is related to the length of therapy. In a pilot study of investigating two months of Maraviroc (300 mg BID) in 11 colorectal cancer patients with metastasis to the liver, Grade 1 dizziness was observed in 1 patient. No patient had dizziness Grade 2 or higher (exposure adjusted rate of 5.1 per 100 pt-yrs). ¹³

Based on experience with the Phase 3 trial, in which both the Maraviroc group and Placebo had exposure adjusted rates of 14.1 versus 17.1, respectively, 6 to 8 patients are expected to experience postural dizziness in a cohort of 40 patients who complete 7 days of therapy. Based on a similar calculation for orthostatic hypotension, we would expect to see less than one patient experience orthostatic hypotension requiring discontinuation of therapy. We recognize that patients with SARS-CoV-2 may be pre-disposed to postural dizziness and orthostatic hypotension because of their illness and poor oral intake, and therefore;

Version #: 2.8 Version Date: 11/6/2020 Page 24 of 30

¹³ Halama N, Zoernig I, Bertel A, et a. Thumoral immune cell exploitation in colorectal cancer metastases can be targeted effectively by anti-CCR5 therapy in cancer patients. Cancer Cell. 2016;29(4):587-601

observed orthostasis is unlikely to be from Maraviroc given the low aforementioned incidence in Phase 3 trials. Furthermore, a study of orthostatic vital signs checked three times in one day in elderly patients admitted to the hospital (most commonly for stroke, infectious diseases, or other reasons) revealed that 2/3 of patients had one set of abnormal orthostatic vitals¹⁴. Therefore, we outline below dose-reduction and stop criteria per patient to address the risk for orthostasis.

Rates, severity, and relationship of postural dizziness, as well as exposure adjusted rates for orthostatic hypotension resulting in discontinuation, will be calculated at the point in which 10 patients have received more than four doses of treatment. The Medical Monitor may request trial stoppage in the instance that an unacceptable rate of discontinuation due to orthostatic hypotension reasonably attributable to Maraviroc is observed.

14.1.1 Dose reduction protocol:

All dose-reductions will be recorded in each subjects CFR.

Patients will be initiated on Maraviroc 300 mg twice daily. Orthostatic vitals will be obtained four hours after the first dose unless otherwise contra-indicated. If symptomatic and orthostatic, the next dose of Maraviroc can be held and inpatient team will be advised to review anti-hypertensive strategy, diuretic use and consider supplemental intravenous fluid if patient is anorexic and dehydrated. Subjects will be re-trialed on 300 mg of Maraviroc the next day. If still orthostatic, the patient will be re-trialed at 150 mg of Maraviroc the next day. Persistent orthostasis probably or definitely attributable (orthostasis that develops after starting Maraviroc that was not present at baseline) may prompt discontinuation of trial medicine with consideration of severity of orthostasis and after discussion with subject and inpatient care team. Withdrawing subjects will be asked to participate in a withdrawal visit as outlined above in section 10.14. Orthostatic vitals will be repeated during course of treatment at the discretion of inpatient care team.

The aforementioned dose reduction protocol will apply to subjects on a moderate or strong CY3PA4 inhibitor, who will be initiated on Maraviroc 150 mg twice daily, with the distinction that dose reduction would occur to Maraviroc 150 mg once daily. For subjects on a moderate or strong CY3PA4 inducer, the subject will be initiated at Maraviroc 600 mg twice daily. If orthostatic as described above, dose-reduction to Maraviroc 300 mg twice daily, followed by Maraviroc 150 mg twice daily will be pursued. Lastly, given the clinical context, intubated and sedated subjects in an intensive care unit will be continued on Maraviroc 300 mg twice without monitoring for postural dizziness of orthostasis. Alternative causes for hypotension in this population should be explored prior to dose reducing Maraviroc.

Version #: 2.8 Version Date: 11/6/2020 Page 25 of 30

¹⁴ Weiss A., Grossman E., Beloosesky Y., et al.(2002) Orthostatic hypotension in acute geriatric ward: is it a consistent finding? Arch Intern Med 162:2369–2374.

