10 EVALUATIONS BY VISIT

10.1 Screening and Enrollment Visit (Day 0)

- Review the study with the subject and obtain written informed consent
- Assign the subject a unique subject number.
- Record demographics data.
- Record relevant medical history.
- Record concomitant medications.
- Perform a complete physical examination.
- Perform a complete review of systems including symptoms of postural dizziness
- Perform and record vital signs.
- Perform and record oximetry on room air and on current oxygen-delivering device.
- Perform and record results of blood pressure testing, including orthostatic vital signs.
- Document and review bloodwork obtained from standard clinical care (chemistry, hematology, hepatic function).
- Collect blood sample for research laboratory test(s): Biomarkers. Collect information on QTc if an electrocardiogram is performed per routine clinical care.
- Document and review chest imaging findings if performed per routine clinical care.

Version #: 2.8 Version Date: 11/6/2020 Page 15 of 30

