Life-threatening (4)	The subject is at risk of death due to the adverse experience as it occurred. This does not refer to an experience that hypothetically might have caused death if it were more severe.

AE Relationship to Study Drug

The relationship of an AE to the study drug should be assessed using the following the guidelines in Table 3. In delineating AE relationship, research team will consider adverse events temporally or otherwise clearly related to administration of the drug in relation to noted deviation from natural history of SARS-CoV-2 infection.

Table 3. AE Relationship to Study Drug

Relationship to Drug	Comment
Definitely	Previously known toxicity of agent; or an event that follows a reasonable temporal sequence from administration of the drug; that follows a known or expected response pattern to the suspected drug; that is confirmed by stopping or reducing the dosage of the drug; and that is not explained by any other reasonable hypothesis.
Probably	An event that follows a reasonable temporal sequence from administration of the drug; that follows a known or expected response pattern to the suspected drug; that is confirmed by stopping or reducing the dosage of the drug; and that is unlikely to be explained by the known characteristics of the subject's clinical state or by other interventions.
Possibly	An event that follows a reasonable temporal sequence from administration of the drug; that follows a known or expected response pattern to that suspected drug; but that could readily have been produced by a number of other factors.
Unrelated	An event that can be determined with certainty to have no relationship to the study drug.

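### Section 14.1.1 explains probably or definitely attributable orthostasis as orthostasis that is merely treatment-emergent, which is a weaker test than Table 3 sets for Probably; the two passages need reconciling

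*Combined protocol and SAP*

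**What the plan says.** Section 14.1.1 sets out a ladder. For a subject started on the standard dose, orthostatic vitals are taken four hours after the first dose. "If symptomatic and orthostatic, the next dose of Maraviroc can be held", and the inpatient team is advised to look at antihypertensives, diuretics and fluids. A re-trial at 300 mg follows. "If still orthostatic, the patient will be re-trialed at 150 mg of Maraviroc the next day". The last step reads "Persistent orthostasis probably or definitely attributable (orthostasis that develops after starting Maraviroc that was not present at baseline) may prompt discontinuation" of the drug, "with consideration of severity of orthostasis and after discussion with subject and inpatient care team".

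Section 11.1 says that Table 3 should be used to assess the relationship of an adverse event to study drug. *Probably* needs plausible timing, a known or expected response pattern, confirmation when the drug is stopped or its dose reduced, "and that is unlikely to be explained by the known characteristics" of the subject's clinical state or by other interventions. *Possibly* covers events with the right timing and pattern that other factors could readily have produced.

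Section 14.1 says that illness and poor intake may predispose these patients to orthostasis, and that "observed orthostasis is unlikely to be from Maraviroc given the low aforementioned incidence in Phase 3 trials". It cites a series of elderly inpatients, checked three times in one day, which "revealed that 2/3 of patients had one set of abnormal orthostatic vitals". The only scheduled baseline check is on Day 0 (Section 10.1): "Perform and record results of blood pressure testing, including orthostatic vital signs".

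**The concern.** Section 14.1.1 borrows the grade names of Table 3 and then explains them by two facts: onset after starting drug, and absence at baseline. Those two facts define a treatment-emergent event. They do not address cause. One event can then carry two different relationships, depending on which section the assessor has open.

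There is also a gap in the other direction. A subject who is orthostatic on Day 0 and worsens on drug does not fit the parenthesis, whatever the cause.

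Relationship to drug is recorded for every adverse event (Sections 9.1.8 and 11.1). The Medical Monitor may ask for the trial to stop if discontinuations for orthostatic hypotension that are reasonably attributable to the drug become too frequent (Section 14.1). That phrase is a third attribution term, and it is not defined. With a single arm, background orthostasis that has been labelled as drug-related cannot be separated later by comparison with a control group. The protocol expects fewer than one orthostatic discontinuation in 40 patients, so one mislabelled case among 16 would be noticed.

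**Working it through.** **1. The two definitions side by side.**

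| Test | Table 3, *Probably* | Parenthesis in Section 14.1.1 |
|---|---|---|
| Timing after drug | Required | Required |
| Known or expected response pattern | Required | Not mentioned |
| Confirmed on stopping or reducing the dose | Required | Not mentioned |
| Unlikely to be explained by clinical state or other interventions | Required | Not mentioned; absence at baseline stands in its place |

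Absence at baseline excludes only orthostasis that was already present on Day 0. It does not exclude orthostasis that the illness brings on later. The dechallenge line is the sharper conflict: orthostasis that persists at the reduced dose has not been confirmed by reducing the dose, yet this is the case that the parenthesis labels as probable or definite.

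**2. The plan's own expected count.** Section 14.1 expects fewer than one orthostatic discontinuation in 40 patients treated for 7 days. Exposure is 40 × 7/365.25 = 0.767 patient-years.
- At the stated 0.07 per 100 patient-years: 0.767 × 0.0007 = 0.0005.
- At 2 of 840 subjects: 40 × 2/840 = 0.10.
- At 0.5%: 40 × 0.005 = 0.20.

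All are below one, so the statement is reproduced. For 16 subjects the last two become 16 × 2/840 = 0.04 and 16 × 0.005 = 0.08.

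**3. How often background orthostasis could reach the last step (illustration).** Inputs: 2/3 abnormal within three checks (Section 14.1), one Day 0 check (Section 10.1), three ladder checks on the standard ladder (after the first dose, at the 300 mg re-trial and at the 150 mg re-trial), and 16 subjects (Section 4.1). Assumptions: the 2/3 means at least one abnormal set in three, it carries over to this population, and there is no drug effect. Reading it as exactly one abnormal set cannot work with independent checks at a common probability, where the maximum is 3 × (1/3) × (2/3)² = 0.444.

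Independent checks: 1 − (1 − p)³ = 2/3 gives p = 1 − (1/3)^(1/3) = 0.307. Normal on Day 0 and abnormal at all three ladder checks: (1 − p)p³ = 0.693 × 0.0288 = 0.020. Over 16 subjects this is 0.32, and the chance of at least one is 1 − 0.980^16 = 28%.

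With within-patient correlation ρ, I used a beta-binomial with s = 1/ρ − 1, a = ms and b = (1 − m)s. The mean m is solved from B(a, b+3)/B(a, b) = 1/3, and the probability is B(a+3, b+1)/B(a, b).

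| ρ | Mean per check | Normal, then three abnormal | Expected of 16 | Chance of at least one |
|---|---|---|---|---|
| 0 | 0.307 | 0.020 | 0.32 | 28% |
| 0.1 | 0.338 | 0.031 | 0.50 | 40% |
| 0.2 | 0.371 | 0.038 | 0.61 | 47% |
| 0.3 | 0.405 | 0.042 | 0.67 | 50% |
| 0.5 | 0.479 | 0.038 | 0.61 | 46% |

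Under these assumptions the figures are upper limits for discontinuation through this one pass of the ladder, because entry also needs symptoms and the last step is discretionary. Even so, the background count could exceed the 0.04 to 0.08 implied by the Phase 3 references.

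**The case against.** The strongest reply is that Table 3 still governs. Section 11.1 says so, and the parenthesis could be read as an onset condition added to the Table 3 grades rather than a replacement for them. That reading is possible but less natural, since the parenthesis follows the grade names as their explanation. If it is what was meant, a clarification costs little.

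Several further points stand and limit the finding.

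- A reader might infer that any orthostasis absent on Day 0 leads to discontinuation. It does not. The step covers persistent orthostasis, after a symptomatic entry, a review of other contributors and two re-trials, and discontinuation only may follow.
- A reader might infer that the parenthesis contradicts the 2/3 series. That series concerns an abnormal set within one day and gives no rate of persistent orthostasis. The protocol cites it as a reason for having the ladder. It shows that a single normal baseline check is a weak reference, which is tension and not contradiction. The clearer conflict, besides Table 3, is with the statement that orthostasis is unlikely to come from the drug.
- A reader might take the size from the first post-dose check: 0.693 × 0.307 = 21%, or 3.4 of 16. That check only opens the ladder, so the figure does not measure the step at issue.
- *Definitely* in Table 3 opens with a known-toxicity limb joined to the rest by *or*. Section 14.1 reports orthostatic hypotension at 600 mg or more, so read literally that limb might admit the event. The clear conflict is with *Probably*.
- Section 12.1 allows discontinuation for any adverse event that the investigator judges to warrant it, and adverse events are recorded whether or not they are related. Worsening in a subject orthostatic at baseline is therefore not hidden; it only lies outside this one definition.

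**Conclusion.** The wording conflict is real and modest in effect. As written, Section 14.1.1 lets persistent illness-related orthostasis be called drug-attributable when Table 3 would support only *Possibly*, with some ambiguity left by the known-toxicity limb of *Definitely*.

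The effect is limited to relationship coding and to the Medical Monitor's judgement of attributable discontinuations. A reader might infer that the primary endpoint is biased. Neither of its two wordings (synopsis and Section 5.1) uses attribution, so the documents do not support that. The interim rate of orthostatic discontinuation is also calculated without an attribution filter.

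The illustrative size is about 0.3 of 16 subjects with independent checks, and 0.5 to 0.7 of 16 with within-patient correlation of 0.1 to 0.5. It rests on carrying an elderly inpatient series over to adults aged 18 and above, on there being no drug effect, and on ignoring symptoms and discretion. Any further orthostatic checks that the inpatient team chooses to make are not counted.

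**What to change.** The sponsor should reconcile the attribution wording in Section 14.1.1 with Table 3 in Section 11.1. This review does not say which discontinuation rule is right. Simply deleting the parenthesis would choose one, because orthostasis that persists after dose reduction would have difficulty meeting the dechallenge test.

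For recording and analysis only:
- code orthostasis that is new, or worse than on Day 0, as treatment-emergent;
- assign relationship separately on Table 3, as for all other adverse events;
- in the interim safety summary, list treatment-emergent and attributed orthostasis separately, with Day 0 orthostatic status noted.

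The cost is a wording change and a few extra lines in a small table. Day 0 orthostatic vitals are already scheduled. The cells will be very small, since the interim look falls at 8 patients in the synopsis and 10 in Section 14.1, so a listing by subject will be more useful than percentages.

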6.3 Exclusion Criteria

- Subjects who are pregnant, breastfeeding, or unwilling to practice birth control during participation in the study.
- Subjects with the presence of a condition or abnormality that in the opinion of the Investigators would compromise the safety of the subject or the quality of the data. This includes, but is not limited to, recent myocardial infarction in past 6 months, neurological, psychiatric, endocrine, or neoplastic diseases that are judged to interfere with participation in the study.
- Subjects with known diagnosis of human immunodeficiency virus infection (HIV)
- Subjects enrolled in another interventional trial (including one for COVID-19) that excludes participation in other trials, or includes a potent CYP3A inhibitor of inducer (e.g. lopinavir-ritonavir)
- Subjects with ESRD or severe renal failure who are taking potent CYP3A inhibitors or inducers

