8.3.1 Dosage/Dosage Regimen

- Maraviroc 300 mg twice a day for patients not on concomitant moderate or strong CYP3A inhibitors/inducers.
- Maraviroc 150 mg twice daily for patients unable to tolerate 300 mg twice daily and for patients on moderate or strong CY3PA inhibitors.
- Maraviroc 600 mg twice daily for patients on moderate or strong CY3PA inducers.

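### The ICU dosing sentence in Section 14.1.1 names 300 mg for every intubated and sedated subject, with no exception for CYP3A-adjusted or already reduced doses

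*Combined protocol and SAP*

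**What the plan says.** Section 8.3.1 sets the dose by concomitant medication and tolerance. Subjects not on a moderate or strong CYP3A inhibitor or inducer receive 300 mg twice daily. The other two levels are "Maraviroc 150 mg twice daily for patients unable to tolerate 300 mg twice daily and for patients on moderate or strong CY3PA inhibitors" and "Maraviroc 600 mg twice daily for patients on moderate or strong CY3PA inducers".

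Section 14.1.1 adds reductions for orthostasis. A subject who started on 300 mg is first re-trialed at 300 mg, and then: "If still orthostatic, the patient will be re-trialed at 150 mg of Maraviroc the next day". Inhibitor users start at 150 mg twice daily and follow the same protocol "with the distinction that dose reduction would occur to Maraviroc 150 mg once daily". Inducer users start at 600 mg twice daily, with "dose-reduction to Maraviroc 300 mg twice daily, followed by Maraviroc 150 mg twice daily will be pursued".

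The paragraph that contains the inhibitor and inducer rules then turns to the ICU and states that "intubated and sedated subjects in an intensive care unit will be continued on Maraviroc 300 mg twice without monitoring for postural dizziness of orthostasis". The word for the interval after *twice* is missing; twice daily is the only sensible reading. One qualifier follows: "Alternative causes for hypotension in this population should be explored prior to dose reducing Maraviroc".

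**The concern.** The ICU sentence takes all intubated and sedated ICU subjects as its group and gives them one dose. It comes directly after the rules that give some of those subjects a different dose, and nothing elsewhere in the protocol says which rule governs in the ICU.

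Followed as written, it would raise the dose of an inhibitor user. It would return most subjects already reduced for orthostasis to a higher dose, and it would halve the dose of an unreduced inducer user. The same sentence waives the orthostasis checks. Section 14.1 itself reports orthostatic hypotension in healthy volunteers at doses of 600 mg or more.

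There is also a compliance problem. Section 13 counts departure from the drug regimen, including the dose-reduction protocol, as a protocol violation. For these subjects, staff cannot tell which dose is the compliant one.

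**Working it through.** The plan gives no figure to reproduce here. The check compares the ICU rule with each dose that Sections 8.3.1 and 14.1.1 assign, and then asks whether the affected subjects can be in the trial.

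**Step 1. Daily dose under the ICU rule.** 300 mg × 2 = 600 mg/day.

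**Step 2. Ratio for each dose state.** Ratio = 600 ÷ assigned daily dose.

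| Dose state | Source | Assigned mg/day | Ratio |
|---|---|---|---|
| No modulator, 300 mg twice daily | 8.3.1 | 300 × 2 = 600 | 600/600 = 1 |
| No modulator, reduced to 150 mg twice daily | 14.1.1; frequency from 8.3.1 | 150 × 2 = 300 | 600/300 = 2 |
| Inhibitor, 150 mg twice daily | 8.3.1, 14.1.1 | 150 × 2 = 300 | 600/300 = 2 |
| Inhibitor, reduced to 150 mg once daily | 14.1.1 | 150 × 1 = 150 | 600/150 = 4 |
| Inducer, 600 mg twice daily | 8.3.1, 14.1.1 | 600 × 2 = 1200 | 600/1200 = 0.5 |
| Inducer, reduced to 300 mg twice daily | 14.1.1 | 300 × 2 = 600 | 600/600 = 1 |
| Inducer, reduced to 150 mg twice daily | 14.1.1 | 150 × 2 = 300 | 600/300 = 2 |

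The ICU rule agrees with 2 of the 7 states and conflicts with 5: three at 2 times the assigned dose, one at 4 times and one at half.

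**Step 3. Can such subjects be in the trial?** Yes.

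- Section 6.3 excludes "Subjects with ESRD or severe renal failure who are taking potent CYP3A inhibitors or inducers". Its only other bar on CYP3A modulators concerns those given within another interventional trial.
- Section 7.1 leaves reducing or stopping a modulator at enrollment to the inpatient team's discretion.
- The prohibited list in Section 7.2 has three entries and no general bar on CYP3A modulators.
- Sections 6.2 and 8.3.3 allow dosing by nasogastric or orogastric tube, so treatment can go on after intubation.
- Intubation is a recorded event at each dosing-day visit in Section 10.

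**Step 4. How many?** This cannot be computed. It needs the share of the 16 subjects who are intubated and sedated within the 7 dosing days and who are also on a modulator or already reduced. The nearest figure is in Section 1: in the lopinavir-ritonavir trial described there, 16% eventually needed mechanical ventilation. If that rate applied here, which is an assumption, 0.16 × 16 = 2.56 subjects would be ventilated at some point. Those affected by the conflict would be a subset of them.

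**The case against.** The strongest reply rests on the verb. A subject on 150 mg or 600 mg cannot be *continued* on 300 mg, so the sentence may cover only subjects on the standard dose, with Section 8.3.1 still governing the rest. The protocol also uses 300 mg as shorthand for the regimen elsewhere: Section 8.1 and the opening of Section 14.1.1 both name 300 mg twice daily without listing the exceptions. This reading is plausible and may be what was meant. It does not repair the text, because the stated group is all intubated and sedated ICU subjects and the sentence closes a paragraph about inhibitor and inducer users. On the narrow reading, the protocol also does not say whether the monitoring waiver applies to anyone on another dose.

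Several further points stand and limit the weight of the concern.

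- **The dose is not wholly fixed.** The following sentence leaves dose reduction open. It deals with hypotension once the subject is in the ICU, however, and does not preserve a CYP3A-adjusted or previously reduced dose.
- **The subset is small.** The subject must give written consent (Sections 6.2 and 9), so will generally have enrolled before sedation. For a standard-dose subject, a reduction follows a failed re-trial and so starts on about Day 3 at the earliest. The fourfold case needs an inhibitor, a failed re-trial, a reduction and then intubation, all within one week. Five of seven counts dose states, not patients.
- **The harm link is indirect.** Section 14.1 refers to doses of 600 mg or more, and the ICU rule gives 300 mg per administration. The link for inhibitor users depends on the assumption that the halved dose is meant to match the exposure of 300 mg alone. In that case 300 mg with an inhibitor would resemble 600 mg without one. For the unreduced inducer user the issue is under-dosing, not hypotension.
- **Other safeguards continue.** They include medication reconciliation (7.1), daily audit of administration records (8.4), daily blood pressure (9.1.5) and daily review of clinical notes for adverse events (9.1.8). They might reveal a mismatch, but none says which dose is right.

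**Conclusion.** The concern holds and should be fixed. As written, the ICU sentence contradicts the assigned dose in 5 of 7 dose states, with ratios from 0.5 to 4, and no other provision resolves the conflict. This rests on reading *twice* as twice daily and on taking the reduced 150 mg dose for subjects without a modulator as twice daily, as Section 8.3.1 indicates. Subjects with no modulator and no earlier reduction are unaffected, as are inducer users already reduced to 300 mg twice daily.

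This is a dosing-safety correction for a small group whose size the documents do not give. It alters no sample size, estimate or analysis and does not threaten the primary endpoint.

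**What to change.** Amend the ICU sentence in Section 14.1.1 so that these subjects stay on their current assigned dose, meaning the CYP3A-adjusted dose from Section 8.3.1 or the dose as already reduced under 14.1.1. The waiver of monitoring for postural dizziness or orthostasis can remain. Removing the figure of 300 mg also removes the incomplete frequency.

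If the investigator and medical monitor do intend 300 mg twice daily to override the other doses in the ICU, the protocol should say so, give the reason and write out the frequency in full.

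The cost is a one-sentence amendment, with no added patients, procedures or analyses.
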